7.4 CT Over-read

The initial CT images and read will be over-read by an attending abdominal radiologist for these reasons:

- 1) Ensure consistency of reports.
- 2) Assess for other vascular injuries that may have been overlooked initially (arterial pseudoaneurysms, arteriovenous fistulas, etc).

The over-read will not replace the initial diagnostic read and will not delay patient care in any way (see section 9 for "Data Collection").

7.5 Patient Follow-up

Patients will be followed for 30 days +/- 3 days after pSAE. For patients still admitted to the hospital, data will be collected from the medical record. For discharged patients with follow-up at UAB, data will be collected from the medical record. For discharges patients without follow-up, the program manager/research coordinator will contact the patient via telephone to collect relevant data (see section 9 "Data Collection").

8. OUTCOMES

Aim 1: Demonstrate feasibility by meeting enrollment and follow-up goals.

Objective 1a: Enroll at least 50% of eligible patients (50 patients total; 25 patients per arm)

Objective 1b: Obtain follow-up in at least 80% of enrolled patients

Aim 2: Assess for similarities and differences between the groups regarding clinical outcomes.

Objective 2a: Compare clinical outcomes of pSAE using coils versus vascular plugs (splenic salvage, immediate/delayed complications, patient length of stay, and post-embolization transfusion requirements)

Objective 2b: Compare technical outcomes of pSAE using coils versus vascular plugs (technical success (defined as the ability to access and embolize the mid-splenic artery), intra-procedural complications, necessity of a secondary embolic to obtain satisfactory hemostasis, and intra-procedural radiation doses)

Objective 2c: Conduct cost analysis of using coils versus vascular plugs (room time, equipment such as catheters, wires, and sheaths, and the cost of the embolic agent itself)

9. DATA COLLECTION

Data is abstracted into an electronic case report form (eCRF) by study staff. The eCRF uses the Research Electronic Data Capture (REDCap) system, a secure research database developed by the NIH. A full list of variables to be collected is shown below. Data logic checks are used to minimize data entry errors.

The following admission parameters will be collected:

- a) Source of patient (transferred from another facility or from the scene of injury?)
- b) Mechanism of injury
- c) Date and time of arrival
- d) Vital signs (temperature, heart rate, blood pressure, respiratory rate)
- e) Use of vasopressors at time of arrival
- f) Intubated at time of arrival
- g) Glasgow Coma Scale (GCS)
- h) Injury Severity Scale (ISS)
- i) Undergoing massive transfusion protocol?

The following blood tests, which are all measured routinely as part of the clinical assessment of trauma patients, are collected, as soon as possible upon arrival:

- a) Arterial blood gas
- b) Hemoglobin and hematocrit
- c) Platelet count
- d) Coagulation parameters including prothrombin time (PT), international normalized ratio (INR), activated partial thromboplastin time (APTT), and Anti-Xa
- e) Thromboelastograph (TEG) or thromboelastogram (ROTEM)

The following data points will be extracted from the initial CT report (emergent):

- a) Phase of enhancement
- b) Splenic injury grade according to AAST guidelines

- c) Signs of accompanying vascular injury such as pseudoaneurysm, extravasation, arterio-venous fistula, or hemoperitoneum
- d) Presence or absence of other intra-abdominal or extra-abdominal trauma

The following data points will be collected from the embolization procedure:

- a) Duration
- b) Radiation dose
- c) Contrast type and volume
- d) Splenic artery diameter
- e) Presence of pseudoaneurysm, arterio-venous fistula, or contrast extravasation on angiography
- f) Embolization material
 - a. Primary (coils vs. vascular plugs)
 - b. Secondary (beads, coils, vascular plugs, foam, other)
- g) Technical success
- h) Intra-procedural complications (non-target embolization, migration of the coil or vascular plug, ineffective treatment requiring splenectomy, vessel rupture, injury at the access site, and splenic infarction/abscess)

The following data points will be collected from the over-read of the CT (non-emergent):

- a) Phase of enhancement
- b) Splenic injury grade according to AAST guidelines
- c) Signs of accompanying vascular injury such as pseudoaneurysm, extravasation, arterio-venous fistula, or hemoperitoneum
- d) Presence or absence of other intra-abdominal or extra-abdominal trauma

The following data points will be collected while the patient is admitted after the embolization procedure:

- a) Amount of blood products required

- b) Length of stay (ICU, floor, and total)
- c) Delayed complications (Abscess, bleeding, infarction, acute kidney injury)
- d) Secondary splenectomy (i.e. splenectomy needed after embolization)

The following data points will be collected at the 30 day follow up:

- a) Delayed complications (Abscess, bleeding, infarction, acute kidney injury)
- b) Secondary splenectomy

...

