14.3.2 Anticipated serious adverse events/serious adverse device effects (SADE)

Anticipated adverse device effects include:

- a) non-target embolization (<1%)
- b) migration of the coil or vascular plug (<1%)
- c) ineffective treatment requiring splenectomy (~10%)
- d) injury at the vascular access site (~1%)
- e) splenic infarction/splenic abscess (~3%)
- f) vessel rupture

Anticipated serious adverse events include:

- a) Given that iodinated contrast is used during the procedure, there is a very low risk for nephrotoxicity or allergic reaction to contrast (~1%).

Anticipated serious adverse events and adverse device effects will also be recorded using the "ELSA Adverse Event Recording Form". In addition, a "ELSA Serious Adverse Event/Serious Adverse Device Effect" form must be completed, and emailed to the ELSA Trial Office within 48 hours. All reports of anticipated serious adverse events/SADE will be forwarded to the medical monitor.

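### Section 9 lists splenectomy and splenic infarction or abscess as intra-procedural complications and again as later outcomes, so one event can count under both Objective 2a and Objective 2b

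*Combined protocol and SAP*

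**What the plan says.** Section 8 splits the Aim 2 comparisons. Objective 2a (clinical) covers "splenic salvage, immediate/delayed complications, patient length of stay, and post-embolization transfusion requirements". Objective 2b (technical) includes "intra-procedural complications, necessity of a secondary embolic to obtain satisfactory hemostasis, and intra-procedural radiation doses".

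Section 9 organises the data by collection window:

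- **Embolization procedure, item h:** "Intra-procedural complications (non-target embolization, migration of the coil or vascular plug", followed by "ineffective treatment requiring splenectomy, vessel rupture, injury at the access site, and splenic infarction/abscess".
- **Hospital stay after the procedure, items c and d:** "Delayed complications (Abscess, bleeding, infarction, acute kidney injury" and "Secondary splenectomy (i.e. splenectomy needed after embolization".
- **30-day follow-up, items a and b:** the same two entries again.

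Section 14.3.2 lists the same six conditions as item h as anticipated adverse device effects. It gives rates for five of them and none for vessel rupture. Section 14.2 sets the adverse-event reporting period from randomization to discharge. Section 11 names tests for categorical variables but does not say whether item h is analysed as one rate or by component.

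**The concern.** Splenectomy for failed treatment, splenic infarction and abscess are mostly recognised after the patient has left the procedure room, and Section 9 itself calls infarction and abscess delayed. Item h nevertheless names them as intra-procedural. This is a stated list that puts them in the wrong place, not an omitted detail.

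Two abstractors could follow the text and code the same patient differently. One enters a later splenectomy only as secondary splenectomy. The other also enters it under item h, because item h names it.

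Aim 2 exists to identify endpoints for a larger trial. If the 2b complication rate partly measures later treatment failure, it may look like a usable technical-safety endpoint, with an event rate to plan on, while largely repeating splenic salvage and delayed complications from 2a.

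**Working it through.** **1. The plan's own figure.** Section 10: 50% of about 100 embolizations a year = 0.50 × 100 = 50 patients, 25 per arm. This reproduces. It is an enrolment target; the protocol gives no power calculation.

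**2. The overlap, from the text.**

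- A splenectomy after an ineffective embolization meets item h (2b). It also meets the secondary splenectomy field, and so would presumably count against splenic salvage (2a).
- An infarction or abscess meets item h (2b) and delayed complications (2a).
- No section gives a time window, attribution rule or count-once rule.

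**3. Inputs for the size (Section 14.3.2).**

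- Procedure-related: non-target embolization <1%, migration <1%, access-site injury ~1%. The <1% rates are taken at 1%. Vessel rupture has no rate and is assumed to be 0 to 1%.
- Disputed: splenectomy ~10%, infarction or abscess ~3%.

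**4. Extreme case: every disputed event entered under item h, and the item analysed as one rate.**

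- Procedure-related sum: 1 + 1 + 1 = 3%, or 4% with rupture at 1%.
- Disputed sum: 10 + 3 = 13%.
- Total: 16% or 17%.
- Disputed share: 13/16 = 81%, or 13/17 = 76%.
- Expected events in 50 patients: 50 × 0.13 = 6.5 disputed, out of 50 × 0.16 = 8 or 50 × 0.17 = 8.5.

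If both <1% items and rupture were near zero, the share in this extreme case would be 13/14 = 93%. The sums treat events as not overlapping within a patient. Under independence, the chance of at least one item h event is 15.3% rather than 16% (16.1% rather than 17% with rupture at 1%).

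**5. How the share depends on data entry.** Let f be the fraction of disputed events entered under item h. The documents do not give f, so it is an assumption shown over its range. Share = 13f / (13f + 3), or 13f / (13f + 4) with rupture at 1%.

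| f | rupture 0% | rupture 1% |
|---|---|---|
| 0 | 0% | 0% |
| 0.10 | 1.3/4.3 = 30% | 1.3/5.3 = 25% |
| 0.25 | 3.25/6.25 = 52% | 3.25/7.25 = 45% |
| 0.50 | 6.5/9.5 = 68% | 6.5/10.5 = 62% |
| 1 | 81% | 76% |

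**6. After the two entries are removed.** Expected item h events are 50 × 0.03 = 1.5, or 50 × 0.04 = 2.0; per arm 0.75 to 1.0. With three independent 1% risks, the chance of no such event in an arm of 25 is 0.99^75 = 47%; with rupture also at 1% it is 0.99^100 = 37%.

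**The case against.** The strongest reply is that the section already separates events by collection window. Item h sits under the procedure and is labelled intra-procedural; secondary splenectomy is labelled as following embolization. A coordinator who follows the labels would enter a splenectomy on day 5 only in the later field. The ~10% and ~3% are anticipated device-effect rates in a section whose reporting period runs to discharge, so they are not intra-procedural rates. Item h has six named components that can be tabulated separately, and nothing says they are pooled. A single splenectomy informing both a complication tally and salvage is not in itself an error.

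Most of this stands, and it limits the size. A reader might infer that every later splenectomy is bound to be counted twice, or that about 80% of the 2b endpoint is contaminated. The documents support neither: the first ignores the collection windows, and the second needs full entry under item h and a pooled analysis that the plan does not specify.

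Two further points stand. Objective 2a already includes immediate complications, so some overlap with 2b is written into the objectives and would survive an edit to item h alone. And closing item h when the patient leaves the room would lose data, because the post-procedure lists have no field for migration, non-target embolization or access-site injury recognised later. Section 7.3 also allows for a technical failure in which the required embolization cannot be done; a splenectomy after that might not fit the present wording of the secondary splenectomy field.

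What the reply does not remove is that item h names these events under the wrong heading and that no rule tells the abstractor what to do.

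**Conclusion.** The concern holds as an avoidable misassignment in the stated item h list. As written, one event can count in both 2b and 2a. The consequence ranges from nothing, if abstractors honour the label, to about 13 of 16–17 percentage points (76–81%) of the item h rate, if all such events are entered there and the item is analysed as one rate. The upper figure assumes the Section 14.3.2 rates apply, the <1% rates are at 1%, rupture is 0–1%, and no patient has two events.

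The damage is confined to Aim 2, which is secondary. Salvage and delayed complications can still be recovered from their own fields, and the primary feasibility aim is unaffected. The change is worth making because it is cheap and keeps the 2b outcome interpretable when endpoints are chosen for the larger trial.

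**What to change.** 1. Remove splenectomy and infarction/abscess from item h. Record them only in the post-procedure and 30-day fields of Section 9, each with an onset date.
2. Define the splenectomy field as any splenectomy after attempted or completed embolization, so that one following a failed attempt is captured.
3. Keep non-target embolization, migration, vessel rupture and access-site injury in item h as procedure-related complications, each with a date of recognition, so that those recognised late are not lost.
4. In Section 11, state that the item h components are reported separately.
5. In Section 8, state that immediate complications in 2a and intra-procedural complications in 2b are the same events, counted once.

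The cost is a small eCRF and wording edit. The reported intra-procedural complication rate will be lower, and with about 1.5 to 2 expected events in 50 patients it will support description rather than comparison.

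### Post-embolization transfusion is counted only during the hospital stay, so follow-up for a compared outcome is unequal and units given at readmission before day 30 are lost

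*Combined protocol and SAP*

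**What the plan says.** Section 8, Objective 2a, names among the clinical outcomes to be compared "patient length of stay, and post-embolization transfusion requirements". Section 1 also lists transfusion as a secondary endpoint.

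Section 9 introduces its variables with "A full list of variables to be collected is shown below". One item there can supply the outcome: "Amount of blood products required". It stands under "The following data points will be collected while the patient is admitted after the embolization procedure". No product, unit, indication or time limit is given.

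The list headed "The following data points will be collected at the 30 day follow up" holds two items: "Delayed complications (Abscess, bleeding, infarction, acute kidney injury") and secondary splenectomy. Blood products are not on it. Section 7.5 sets follow-up at 30 days, with three days' tolerance either way.

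Before embolization, the only transfusion item is the admission question "Undergoing massive transfusion protocol". Section 11 compares continuous variables by Student's t-test; its multivariable models are for splenic salvage, not transfusion.

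**The concern.** A count compared between arms needs the same period of observation in every patient, or an analysis that allows for unequal periods. Here the period ends when the patient goes home. Length of stay arises after randomization, may be affected by the device, and appears beside transfusion in the same objective.

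Three consequences follow. Blood given for a re-bleed counts if the patient is still in hospital and not if the patient has left and come back. Patients with other injuries can accrue units unrelated to the spleen, and more of them the longer they stay. Red cells, plasma and platelets are not separated, and no quantity given before embolization is recorded against which to read the later amount.

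The stake is Aim 2, which is meant to identify endpoints for a larger trial. A mean and SD gathered over unequal windows would be a poor basis for choosing transfusion as an endpoint or for planning on it.

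**Working it through.** The plan gives no transfusion mean, SD, effect size or power to reproduce. Its only sample-size figure is the recruitment target in section 10: 50% × 100 procedures = 50 patients, 25 per arm. That reproduces, but it was not derived from this outcome.

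**1. The section 9 lists side by side**

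| Item | During the stay | At day 30 |
|---|---|---|
| Blood products | yes | no |
| Delayed complications, including bleeding | yes | yes |
| Secondary splenectomy | yes | yes |

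A re-bleed after discharge is thus kept as an event while its transfused amount is lost. Adverse event reporting (section 14.2) stops at discharge and does not recover it. For a patient still in hospital at day 30, the text does not say whether counting stops then or at discharge.

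**2. Effect of uncounted units.** Take two patients who re-bleed on the same day after embolization and receive the same blood. One is still an inpatient and contributes those units; the other has been discharged and readmitted and contributes none. If k units go uncounted in an arm of 25, the arm mean is too low by k/25, or 1/25 = 0.04 per unit. The difference between arms is off by (k₁ − k₂)/25, which is zero only if both arms lose the same number. The documents give no basis for k.

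**3. Dependence on stay (illustration).** Assume the same rate r of units per inpatient day in both arms and mean stays L₁ and L₂. The difference in admission totals is r × (L₂ − L₁). With r assumed at 0.1 to 0.3:

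- stays of 6 and 8 days: 0.1 × 2 = 0.2 to 0.3 × 2 = 0.6 units;
- stays of 5 and 10 days: 0.1 × 5 = 0.5 to 0.3 × 5 = 1.5 units.

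This shows that the total moves with stay. It does not estimate a bias in this trial. Where discharged patients receive no blood, a count to day 30 gives the same difference; it would then describe units actually given over equal follow-up.

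**4. Noise from other injuries (illustration).** Let f be the share of total variance due to blood given for other injuries, and set the SD of splenic-related units to 1. The SD becomes s = 1/√(1 − f). With 25 per arm and two-sided α = 0.05 (sidedness assumed), the difference detectable with 80% power is (1.960 + 0.842) × √(2/25) × s = 0.792 × s. Power for a difference of 0.8 is Φ(0.8/(s × √(2/25)) − 1.960).

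| f (assumed) | s | Detectable difference | Power at 0.8 |
|---|---|---|---|
| 0 | 1.000 | 0.79 | 81% |
| 0.25 | 1.155 | 0.92 | 69% |
| 0.50 | 1.414 | 1.12 | 52% |
| 0.75 | 2.000 | 1.59 | 29% |

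The documents do not give f, so the table shows a range and not a finding.

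**The case against.** The case for leaving this alone has real content.

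- **Randomization balances other injuries on average.** True. Blood given for them is mainly noise, although chance imbalance is plausible at 25 per arm. Section 6.3 narrows the mix further, since stable patients whose other injuries need abdominal surgery typically go to operation. Extra-abdominal injuries remain, and section 6.2.2 does not exclude them.
- **Injury burden and arrival status are recorded.** Also true: injury severity, other trauma, hemoglobin, platelets, coagulation and vital signs are all in section 9. They could support an adjusted analysis, but section 11 plans none for this outcome, and none is a quantity of blood given.
- **Re-bleeding after discharge is captured.** Bleeding and splenectomy are, to day 30. Only the amount transfused is lost, but that amount is the outcome.
- **The text may be broader than it looks.** Section 9 does not say which admission, and its last list ends in an ellipsis, so a further item cannot be wholly excluded. Against this, a separate 30-day list exists without blood products, and no other section mentions transfusion after discharge.
- **A short fixed window would be no better.** A cut-off such as 72 hours gains precision only if splenic transfusion falls inside it. The plan itself treats delayed bleeding as an outcome, so such a window drops late re-bleeds. This stands, and it is why an early window should be supplementary.
- **It is a pilot.** The primary outcome is feasibility, and Objectives 1a and 1b are untouched. This limits the weight of the point but does not remove it, given what Aim 2 is for.

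**Conclusion.** The point holds. As written, a compared outcome has unequal follow-up: each patient's transfusion window is the length of stay, and units at a readmission before day 30 are not counted, while related events are followed to day 30. This adds noise to an unadjusted comparison of 25 with 25. It can also bias that comparison if length of stay or timing of re-bleeding differs by device; whether either does is unknown.

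The size cannot be computed from the documents. The only figure free of outside assumptions is 0.04 units in an arm mean for each uncounted unit. The conclusion rests on reading the in-hospital list as the admission for embolization and on taking section 9 at its word that its list is full.

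A reader might infer that the outcome reflects length of stay and injury burden more than splenic bleeding, or that a definite loss of precision can be attached to the admission window. The documents support neither. They give no transfusion rates or stay lengths, and any such figure depends on assuming when splenic units are given and how other transfusion varies between patients. This should be corrected, but it does not threaten the primary aim.

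**What to change.** Define the outcome in section 8 as red-cell units given from the end of embolization to day 30, over the same window in every patient whether in hospital or discharged. In section 9:

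- list plasma and platelet units separately;
- add blood products given at any readmission to the 30-day list;
- record red-cell units from arrival to embolization as a baseline value.

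An early count, for example over 72 hours, can be reported as a supplementary measure, and the admission total kept as descriptive.

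The cost is one outcome sentence and a few eCRF fields. Two limits remain. Counts may be incomplete for readmissions elsewhere that are known only by telephone, so their completeness should be reported. A common window also does not remove blood given for other injuries; that stays as noise, which the baseline count and recorded injury severity help to describe.

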10. RECRUITMENT TARGETS

Our group performs approximately 100 SAEs in a 12 month period. Thus, we will consider having enrolled at least 50% of the SAE patients (50 patients total; 25 patients/arm) as success.

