3. INTRODUCTION/ BACKGROUND

Trauma is the leading cause of death and disability in the United States for all age groups and the single most important cause for years of life lost for persons under the age of 65 [1]. As a major, urban, academic medical center, UAB Hospital is one the busiest trauma centers in the country treating approximately 4,500 major trauma patients annually. Many of these patients present with significant abdominal injuries. Major abdominal trauma, whether by blunt forces or penetrating injuries, carries a significant risk for patient mortality. The spleen is one of the most commonly injured organs in abdominal trauma [1]. Hemodynamically unstable patients whose primary site of injury is the spleen require splenectomy. However, the management of hemodynamically stable patients with traumatic injuries to the spleen is less well-defined. The recognition of the key role of the spleen in producing antibodies, monocytes, and activated lymphocytes has led to a paradigm shift in the management of splenic injuries towards preservation when possible. Currently, the majority of patients with splenic injury are managed without surgery [8].

Splenic preservation rates are improved for patients with high-grade splenic injuries when NOM is supplemented by image-guided, trans-catheter splenic artery embolization (SAE) [3-6]. SAE is currently the standard of care for hemodynamically stable patients with high-grade splenic injuries. SAE is primarily performed using proximal splenic artery embolization (pSAE). pSAE is most often accomplished using either coils or vascular plugs as the embolic agent, both of which are FDA-approved.

Coils have a long history of efficacy and safety for embolization and are thus familiar embolic agents to most endovascular specialists. Further, coils large enough to embolize the mid-splenic artery can be deployed through a standard micro-catheter, which means they can be used in even the most tortuous splenic arteries. However, multiple coils may be needed in the same patient to achieve hemostasis in the mid-splenic artery. This attribute may increase overall cost, iodinated contrast use, procedural time, and the radiation exposure to the patient and medical staff. Additionally, given the high-flow nature of the splenic artery, even an appropriately sized coil may migrate distally. Some of these limitations are overcome through the introduction of coils that are both longer

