and larger than traditional coils, namely POD® coils (Penumbra, Alameda, CA, USA). Using these larger coils can decrease the number needed to obtain hemostasis. These coils come in two varieties: 1) a helical coil sized to the vessel diameter that anchors the coil pack in the high-flow vessel thereby reducing the risk of distal migration and 2) a packing coil that is used to fill in the spaces within the helical coil. A typical pSAE using coils will involve the deployment of one helical coil followed by multiple packing coils until hemostasis is achieved.

Vascular plugs attempt to overcome the limitations of coils. For example, the deployment of a single vascular plug can typically provide hemostasis in the mid-splenic artery, theoretically reducing procedural time, contrast load, and radiation exposure. Despite this, vascular plugs are usually less familiar devices to endovascular specialists. Another drawback of vascular plugs is that they cannot be deployed through a standard micro-catheter but rather require the advancement of a larger, stiffer 0.035 inch system into the mid-splenic artery. This may limit their use in very tortuous splenic arteries. Vascular plugs reaching up to 8mm in size (Amplatzer™ IV, Abbott Medical, Abbott Park, IL, USA) can be deployed through a standard 5F diagnostic catheter. Larger vascular plugs (Amplatzer™ II) require at least a larger 6F guiding catheter.

Currently, the selection of embolic agent for pSAE is primarily based on operator experience and preference. The efficacy, technical success, and cost of using coils compared to vascular plugs has been evaluated in such conditions as pelvic congestion syndrome [10], yet, to the best of our knowledge, these embolic agents have never been compared for their use in pSAE, much less in a randomized, prospective fashion. We anticipate this pilot trial to demonstrate the feasibility of a larger study and provide sufficient information to identify appropriate primary endpoints. The innovation of this proposal is strengthened by the inclusion of over-reads of pre-procedural CT scans, which will allow accurate grading of splenic injury and information regarding associated vascular injury to the spleen. If found, significant differences between our study groups in either clinical outcomes, technical parameters, or cost would have an immediate impact on how we care for trauma patients both locally and nationally.

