4. AIMS AND OBJECTIVES

Aim 1: To demonstrate the feasibility of performing a trial of pSAE in trauma patients with splenic injuries (see section 8 “Outcomes”).

Objective 1a: To demonstrate that at least 50% of eligible patients can be enrolled into a randomized clinical trial.

Objective 1b: To demonstrate that successful follow-up at 30 days will be obtained in at least 80% of enrolled patients.

Aim 2: To evaluate clinical outcomes in order to identify endpoints for a larger trial (see section 8 “Outcomes”).

[figure not shown]
Objective 2a: To compare clinical outcomes of pSAE using coils versus vascular plugs.

Objective 2b: To compare technical outcomes of pSAE using coils versus vascular plugs.

Objective 2c: To conduct a cost analysis of using coils versus vascular plugs.

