7.3 Proximal Splenic Artery Embolization Procedure

An attending interventional radiologist will perform all SAE procedures using either moderate conscious sedation or general anesthesia depending on the patient's condition. The vascular access site is prepared and draped in standard sterile fashion.

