13. HUMAN SUBJECTS RESEARCH

13.1 FDA Requirements

This study will enroll 50 patients with splenic injuries. The study interventions are approved by the Food and Drug Administration (FDA) as a Class 2 under 21 CFR 892.1600. Because it is a nonsignificant risk device being used in accordance with its defined indications, an FDA Investigational Device Exemption (IDE) is not required.

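### The accrual criterion for the primary feasibility outcome uses two denominators, eligible patients and SAE patients, and equates both with 50 patients

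*Combined protocol and SAP*

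**What the plan says.** Section 11 names feasibility as the primary outcome but adds no criterion for it. The accrual criterion appears in three places:

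- Section 4, Objective 1a, aims to show that "at least 50% of eligible patients can be enrolled into a randomized clinical trial". Aim 1 there refers the reader to Section 8.
- Section 8, Objective 1a, gives the percentage and a count together: "Enroll at least 50% of eligible patients (50 patients total; 25 patients per arm".
- Section 10 starts from volume, "Our group performs approximately 100 SAEs in a 12 month period", and concludes: "Thus, we will consider having enrolled at least 50% of the SAE patients (50 patients total; 25 patients/arm) as success".

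Section 13.1 repeats the total: "This study will enroll 50 patients with splenic injuries". The study calendar in Section 5 gives a 12-month enrolment period, January to December 2019. Section 14.4 plans to keep enrolling until 25 patients in each arm have follow-up.

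**The concern.** Sections 8 and 10 give the same count but take half of different groups. Section 6.3 puts the judgement that a patient is a candidate for SAE first and the eligibility screen after it. Section 6.2 then limits entry to adults with grade III or higher traumatic injury who will have proximal embolization, and adds seven exclusions. Eligible patients are therefore a subset of SAE patients, and one number cannot in general be half of both.

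The result is meant to support further work: "We anticipate this pilot trial to demonstrate the feasibility of a larger study". If the two percentages, or a percentage and the count, point in different directions, the same enrolment could be reported as success or as failure. The choice could then be made after the enrolment figures are known.

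**Working it through.** **Inputs.** N, the number of SAEs in 12 months: about 100 (Section 10). Required share: 50% (Sections 4, 8 and 10). Count: 50, or 25 per arm (Sections 8 and 10). Window: 12 months (Section 5). E, the number eligible in the window: not given in the visible text, so assumed below. n: patients enrolled in the window.

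**Step 1. The plan's own figure.** 0.5 × 100 = 50, and 50 / 2 = 25 per arm. The figure reproduces with all SAEs as the denominator.

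**Step 2. The eligible denominator at N = 100.** The eligible percentage is met when n ≥ 0.5 × E. The SAE percentage is met when n ≥ 0.5 × 100 = 50, which is also the count.

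| E (assumed) | 0.5 × E | n meeting the eligible percentage but missing the SAE percentage and the count | 50 / E |
|---|---|---|---|
| 100 | 50 | none | 50.0% |
| 90 | 45 | 45-49 | 55.6% |
| 80 | 40 | 40-49 | 62.5% |
| 70 | 35 | 35-49 | 71.4% |

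The table shows where the rules part, not how likely that is.

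**Step 3. Direction.** Since E ≤ N, 0.5 × E ≤ 0.5 × N. Meeting the SAE percentage therefore implies meeting the eligible percentage, but not the reverse.

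**Step 4. Section 10 on its own, when N is not 100.** Volume is stated only as approximate.

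- N = 90 (assumed): 0.5 × 90 = 45. Enrolling 45-49 meets Section 10's percentage and misses its count.
- N = 110 (assumed): 0.5 × 110 = 55. Enrolling 50-54 meets the count and misses the percentage (50 / 110 = 45.5%; 54 / 110 = 49.1%).
- N = 110 and E = 100 (both assumed): 0.5 × 100 = 50, so 50 is exactly half of the eligible patients although 110 − 100 = 10 SAE patients are ineligible.

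**Step 5. Time.** No success criterion cites the 12-month window, and Section 14.4 lets enrolment run on. Suppose 80 are eligible and 35 are enrolled by month 12 (assumed): 35 / 80 = 43.8%. Enrolling 50 − 35 = 15 more later brings the count to 50, but the percentage for the window stays at 43.8%.

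**The case against.** Four points can be made for the plan as it stands.

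- **The SAE patients may be loose shorthand for the study population.** Section 3 introduces SAE in the setting of splenic injury and says that "SAE is primarily performed using proximal splenic artery embolization (pSAE". Section 7.3, on the study procedure, says that "An attending interventional radiologist will perform all SAE procedures". This has weight: the proximal requirement, and perhaps the trauma and grade requirements, may remove few patients. It does not close the gap, because age and the exclusions remain, and Section 6.3 treats eligibility as a filter applied after SAE candidacy.
- **Section 4 is not a free-standing rule.** It defers to Section 8. This stands, and the conflict is therefore between Sections 8 and 10, and between percentage and count within each.
- **The count is stable.** Sections 8, 10 and 13.1 agree on 50, and Section 14.4 on 25 per arm. With enrolment allowed to continue, a final total below 50 may never arise. The 12-month calendar pulls the other way, and a count reached late says little about the share enrolled.
- **The gap is unknown.** This stands. No figure in the documents shows it to be large. The CONSORT diagram is not visible, so nothing can be said about what it contains.

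A reader might also infer that 50 is miscalculated, or that any total below 50 fails Section 10 outright. The documents support neither. The arithmetic is right for its own denominator, and with 90 SAEs Section 10 would be split, not simply failed.

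**Conclusion.** The accrual threshold for the primary outcome is wrong as written, because it is internally inconsistent. Two denominators carry one count, and the visible text does not rank them or say whether percentage or count decides. Confidence in the inconsistency is high.

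Confidence about how often the rules would split is low. With exactly 100 SAEs, all of them eligible, the rules coincide. With 90, 80 or 70 of 100 eligible, they split over 5, 10 or 15 possible enrolment totals (49 − 45 + 1, 49 − 40 + 1, 49 − 35 + 1). These eligible shares are assumptions. A reader might infer that a contradictory result is likely, or that 50 can be half of the eligible patients only if every SAE patient is eligible. The first has no support in the documents. The second holds only at exactly 100 SAEs, and the plan says approximately.

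In a 50-patient pilot with a consistent count and an unknown gap, this should be fixed, and before the accrual result is read.

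**What to change.** Use one accrual criterion in Sections 4, 8 and 10: at least 50% of the patients who are eligible under Section 6.2 during the 12-month enrolment window are enrolled. State that this percentage decides accrual success.

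Define the denominator explicitly. Patients or representatives who are approached and decline count as eligible but not enrolled. State that exclusion 6.2.2(a) covers only the situation described in Section 6.3, where the patient cannot consent and the representative is not physically present. Otherwise refusals could be read as ineligible, which would inflate the percentage.

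Give 50 patients (25 per arm) as a separate recruitment target based on SAE volume, not as the equivalent of half of the eligible patients. Do not count patients enrolled after month 12 under Section 14.4 towards the 12-month accrual result.

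The cost is mainly wording. Reasons for non-enrolment must be logged during the screening that research associates already do for all grade III or higher injuries. The trial may meet the percentage and miss the count, or the reverse; with the percentage named as deciding, that outcome has a reading fixed in advance. Reporting the share enrolled among all clinically suitable patients, including those lost because consent could not be obtained, is optional and not part of this fix.
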